To our knowledge, no trials in adults have compared pump treatment with injections where the same structured training in insulin adjustment has been given, so the added benefit of the pump technology is still unclear. There is an urgent need to establish this, and identify patients who benefit the most. This will enable the Department of Health (DH) via NICE to calculate the proportion of adults with Type 1 diabetes that would benefit from pump therapy to guide the commissioning bodies that are expected to provide funding. A randomised controlled trial is needed to establish these outcomes without bias.

The DAFNE (Dose Adjustment for Normal Eating) course is a 1-week structured course teaching skills in insulin self-adjustment and carbohydrate counting, currently being delivered in over 78 centres across the UK and Ireland (with over 17,500 individuals now trained)(2). We propose a novel study in which adults waiting for a DAFNE course are randomly allocated to undertake either the standard course with injections or DAFNE incorporating use of pump therapy. The investigators involved in this study are already undertaking research into other aspects of DAFNE: measuring cost-effectiveness, identifying which components are crucial, and factors determining which DAFNE patients manage their diabetes more effectively. We have obtained funding to pilot a combined DAFNE and pump course and we will use this work to refine the curriculum, ensure that the measurements we want to make are feasible and estimate likely recruitment rates. The applicants have expertise in structured Type 1 diabetes education, pump therapy (having trained in total over 500 pump patients) and in health economic assessment of diabetes interventions.

The aim of our trial will be to establish for patients, professionals and those funding the service, the added benefit of using a pump during intensive insulin therapy. The applicants have been involved in the NICE appraisal of insulin pumps, been members of NICE appraisal committees and have a good understanding of what evidence NICE needs. Our aim is to inform the next NICE reviews of insulin pumps and structured education.

We will conduct this trial in compliance with the protocol, GCP and regulatory requirements.

2. Aims and objectives

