The 5-day structure of the adult DAFNE course and additional follow-up sessions have been maintained while modifying the course to incorporate the additional skills and learning outcomes of CSII therapy. Thus the principles of insulin dose adjustment taught on the adult course are maintained. The additional components of the course have been modelled informally during existing CSII courses in the participating centres and in a pilot study which has been run in 3 centres. The need to introduce CSII skills requires the addition of a pre-course session, which will be run approximately 2 weeks before the DAFNE course. It is important that any skills for use of CSII are taught entirely separately from the course principles since we need to ensure that CSII participants do not get any extra tuition compared to the MDI participants in order to minimise bias. The participant will learn to use the pump on saline from the point of the pre-course session for CSII skills, and will be asked to switch to insulin on the evening before the DAFNE course. Clinical care would continue for patients as normal after the course. Participants will also be given contact details of the educators, as they would for a standard DAFNE course, in case they wanted to contact a clinician for advice on an ad hoc basis.

Minimisation of Bias

In addition to both courses being run over equal time span, bias will be minimised through:

- 1. Ensuring that participants in both arms of the study have a bolus calculator to work out the amount of insulin they should be taking.
- 2. Participants in both arms of the study recording insulin usage/dose through use of a recall question rather than recording directly. This is because a pump would automatically record insulin used, meaning that measurements across the arms are likely to be different methods if we asked participants to record the actual measures.
- 3. Fidelity testing to ensure that the principles of insulin adjustment are delivered in a similar fashion for both CSII and MDI courses.

Fidelity Testing

Fidelity testing will be carried out to ensure that the courses are delivered according to DAFNE philosophy and principles and that the educators delivering the courses have

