the skills to deliver these principles. Since there is already a robust system being used for quality assurance of the MDI courses and these will have already been audited, it is only the CSII courses that will need to be audited in order to check that they run to the same standard.

An experienced DAFNE educator from one of the participating trusts will be employed as an auditor. The auditor will visit each site to observe one of the courses on a Wednesday. Wednesday has been chosen since both the nutrition and diabetes expert that teach on the course will deliver parts of the course on that day. Patients on the course should have settled into the course and be more relaxed by the 3rd day. The auditor will assess that the staff are appropriately trained within the trust and the session delivery. This will be completed through assessment of whether the correct DAFNE content is delivered, whether it is delivered in the correct order and whether the best methods of delivery are used. The educator will be assessed according to certain criterion in a peer support core skills form.

[figure not shown]
Once the auditor has completed the assessment, feedback will be given in order that the trust and the educators may resolve any problems and the assessment sheets will be kept on file so that any differences in course delivery between the arms of the study may later be identified.

8. Assessments and procedures

Data Collection Procedure

Once participants have been enrolled and allocated a course date, the data collection process starts. Data collection occurs at baseline, course, 6 month, 1 year and 2 year visits. The process includes a post course and 6 month interview for those participants who have consented to and been selected for the qualitative psychosocial element of the study. The participants will be sent data collection documents to fill out approximately 2-6 weeks before the 6 month, 1 year and 2 year visits and are given reminder letters, phone calls or texts prior to the visit. This is so that the patients may bring the completed forms with them to the visit thereby maximizing the return of data. CRFs are filled out by the educator in an interview style at the visit.

Figure 5 and table 1 below outline the data collection process, instruments collected and outcomes of the study covered.

[figure not shown]

Table 1. Documents for Data Collection

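### Fidelity testing is presented as a bias control across both arms, but trial assessment sheets are planned for CSII courses only, so the trial's own fidelity data cannot compare delivery between arms

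*Protocol*

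**What the plan says.** The Introduction gives as the reason for the trial that "no trials in adults have compared pump treatment with injections where the same structured training in insulin adjustment has been given". Section 7, Minimisation of Bias, then names as its third control "Fidelity testing to ensure that the principles of insulin adjustment are delivered in a similar fashion for both CSII and MDI courses".

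The Fidelity Testing part of section 7 sets out how this is done. It gives a reason for leaving out the control arm, "Since there is already a robust system being used for quality assurance of the MDI courses and these will have already been audited", and concludes that "it is only the CSII courses that will need to be audited in order to check that they run to the same standard". An educator employed as auditor does the work: "The auditor will visit each site to observe one of the courses on a Wednesday". Delivery is scored on a peer support core skills form. Afterwards "feedback will be given in order that the trust and the educators may resolve any problems", and the sheets are filed "so that any differences in course delivery between the arms of the study may later be identified".

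**The concern.** The protocol claims a property that its procedure does not have. It says that fidelity testing covers both arms and that the filed sheets will reveal differences between them, yet it plans sheets for one arm only.

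Similar training is the condition under which an HbA1c difference can be read as the added benefit of the pump. The Introduction itself hypothesises that much of the apparent benefit of pumps may come from retraining. The sample size section allows for clustering by educator, with an ICC of 0.05, so the protocol accepts that delivery may affect the primary outcome. A reader of the trial report who asks whether the two arms were taught alike would be pointed to fidelity data that cannot answer.

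A second, smaller matter is that the audit is not passive. It ends in feedback meant to put problems right and, within the trial, that feedback follows CSII courses only.

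**Working it through.** The point is mainly one of reading. The only arithmetic is audit coverage, and the protocol states no coverage figure to reproduce.

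**Inputs**
- 48 courses randomised across 8 sites (section 6, Randomisation).
- At least 3 CSII and 3 MDI courses per site (Trial Summary).
- One course observed per site, on one day, among CSII courses only (section 7, Fidelity Testing).
- Two to seven additional courses foreseen (section 9, Review of sample size in August 2012).
- Assumption: courses split equally between arms.

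**Coverage**
- Courses per arm: 48 / 2 = 24, which agrees with 8 sites × 3 = 24.
- CSII courses observed: 8 sites × 1 = 8, so 8 / 24 = 33%.
- MDI courses observed: 0 / 24 = 0%.
- All courses: 8 / 48 = 17%.
- With the additional courses the total is 50 to 55, or 25 to 27.5 per arm. CSII coverage becomes 8 / 25 = 32% down to 8 / 27.5 = 29%. The MDI figure stays at zero.

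**The statements side by side**

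| What is claimed | What is planned |
|---|---|
| Fidelity testing covers both CSII and MDI courses (Minimisation of Bias) | Only CSII courses are audited (Fidelity Testing) |
| Filed sheets allow differences between arms to be identified (Fidelity Testing) | Sheets come from audited courses, hence from CSII only |

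A between-arm difference needs a measurement in each arm. With none planned in the MDI arm it cannot be computed from these sheets, however many CSII courses are observed.

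**Does the existing MDI quality assurance fill the gap?** It would need to cover courses run within the trial, use a comparable instrument, and yield records that the trial can obtain. The protocol states none of the three. It does not rule them out either, so the gap lies in what is specified.

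**Feedback.** It is given after an audit, so within the trial it follows CSII courses. It goes to the trust and the educators, and every site runs both kinds of course. Whether the same educators teach both arms is not stated. If they do, some of the feedback would carry over to MDI courses. The document gives nothing from which to estimate an effect on HbA1c, so no number is put on it here.

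**The case against.** The case for the plan is a fair one. The standard course is an established benchmark with its own quality assurance, and the pump course is the modified version. Checking the new version against the old standard is coherent, and preferring concurrent observation of both arms is partly a matter of taste. Equal training also rests mainly on other features: the same five-day structure, the same principles of dose adjustment, pump skills taught in a separate pre-course session, and shared sites. All of this stands. It does not rescue the statement that filed sheets will show differences between arms.

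Four stronger readings are tempting, and the document does not support them.

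- *There is no between-arm information on delivery at all.* The qualitative study interviews around 20 participants per arm about the course, plus 12 educators about what took place, and compares the accounts of participants from CSII and MDI courses. A questionnaire at two years asks about adherence to DAFNE principles. None of this replaces observation, but it is not nothing.
- *MDI courses receive no audit or feedback.* The routine scheme may provide both; the protocol does not say.
- *Feedback biases the result towards CSII.* The audit is meant to bring the modified course up to the existing standard, so it could equally bring the arms closer together.
- *The trial repeats the unequal education criticised in earlier trials.* The Introduction criticises unequal amounts of education. Section 7 addresses amount through equal course length and separate pump training. Quality of delivery is a different matter.

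**Conclusion.** The point holds as an internal contradiction about a bias control. The trial's own fidelity data will cover about 8 of 24 CSII courses and no MDI courses, so they cannot show whether delivery differed between arms. The CSII figure assumes an equal split of 48 courses and one visit per site; it falls slightly if courses are added. The MDI figure follows from the text alone.

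One-sided feedback is a real asymmetry within the trial, but its effect on HbA1c is unknown in size and direction and may be diluted by carry-over. A reader might infer that an HbA1c difference could then not be attributed to the pump. That goes too far: the design gives other grounds for believing that training was similar. What is missing is direct verification by observation in the MDI arm, and the protocol should not imply that it has this.

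**What to change.** Amend the Fidelity Testing part of section 7 so that the existing DAFNE quality audit at each site is timed to a trial MDI course, uses the same peer support core skills form and the same feedback rule as the CSII audit, and is reported by arm. The cost is protocol wording and some scheduling effort. It assumes that a routine audit can be placed within the trial period at each site, which the protocol does not say.

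Two other routes cost more. One extra observed MDI course per site means about eight more auditor days. Dividing the eight planned visits between arms would halve the checking of the newer course.

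If no MDI trial course is to be observed, or the courses have already been run, withdraw the between-arm statements from both Minimisation of Bias and Fidelity Testing. State instead that equal delivery was not directly verified by observation in the MDI arm. This costs only wording.

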Post 6 Months, 1 year, 2 year	Post diary instructions	Sent out 4 weeks prior to 6 month, 1 year & 2 year visits	Not collected	Educators	Biomedical measures	Moderate hypoglycaemic episodes for next 4 week period
Post 6 Months, 1 year, 2 years	Post hypoglycaemia recall log	6 month, 1 year & 2 year visits	6 month, 1 year & 2 year visit	Educators – filled out in conjunction with diary	Biomedical measures.	Moderate hypoglycaemic episodes for preceding 4 week period
Post 6 Months, 1 year, 2 years	Blood and urine samples	6 month, 1 year & 2 year visits	6 month, 1 year & 2 year visit	Laboratory	Biomedical measures	HbA1c & lipids, proteinuria & albumin-creatinine ratio at 1 and 2 years but not 6 months
Post 6 Months, 1 year	Post Psychosocial questionnaire pack (see entries for baseline pack above for separate questionnaires included except for exclusion of baseline demographics and change to DTSQc questionnaire at 1 year)	Sent out approximately 2-6 weeks prior to 6 month & 1 year visits	6 month & 1 year visit	Educators	Quantitative psychosocial, health economics	See entries for baseline pack above for all outcomes covered

Time Period of Study	Collection Tool	When Sent/Given to Patient	When Collected	Who Collects	Which Element(s) of the Trial Relevant for	What Outcome is Covered
Post 2 years	Post Psychosocial questionnaire pack (see entries for baseline pack above for separate questionnaires included) except for the following changes: - Exclusion of baseline demographics - Inclusion of DAFNE principles, use of bolus calculators and use of pump features	Sent out approximately 2-6 weeks prior to 2 year visit	2 year visit	Educators	Quantitative psychosocial, health economics	All outcomes included in the psychosocial questionnaire pack with the addition of: - DAFNE principles - Use of bolus calculators - Use of pump features
Ongoing collection	Severe hypoglycaemia episodes log	Ongoing collection by telephone and CRFs at each visit	Ongoing collection by telephone and CRFs at each visit	Educators – filled out in conjunction with diary	Biomedical measures.	Severe hypoglycaemia episodes throughout duration of the trial
Ongoing collection	AE Identification log	Ongoing collection by telephone and CRFs at each visit	Ongoing collection by telephone and CRFs at each visit	Educators	Biomedical measures	Safety endpoints

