Two analyses, one within the trial, and another using a lifetime analysis based on the Sheffield Type 1 Diabetes Policy Model (currently in development through the NIHR Programme Grant), will be undertaken. For the within trial analysis (and hence those parameters that will subsequently be used in the Policy Model), missing data will be imputed with multiple imputation within STATA using ICE. An incremental cost effectiveness ratio (ICER) will be calculated with uncertainty around this characterised by plots on the cost-effectiveness plane and its associated cost-effectiveness acceptability curve and frontier. Deterministic sensitivity analysis will examine the effect of calculating QALYs using the SF-6D as based on the SF12 data. Sub-group analyses will be undertaken using the same populations as used within the clinical analysis, namely, for participants with HbA1c level below and ≥7.5% (58mmol/mol).

Site & Trial Closure Procedures

At the point at which all questionnaires and CRF's have been collected and entered (or participants have failed to respond despite reminders) and all data have been entered and cleaned, closure of the database will be approved. The end of the trial is defined by the point at which all questionnaires are returned and entered (not at last patient last visit) since the participants may return questionnaires after the visit. Questionnaire data will make up a significant proportion of the trial data.

Trial Pharmacovigilance

The safety of trial participants is of utmost importance and as such MHRA legislation and Sheffield CTRU SOPs will be followed in order to conduct the trial safely and to be able to assess any adverse events or serious adverse events that may occur during the trial. The following section outlines the methods for ensuring and assessing participant safety:

Definitions

The Medicines for Human Use (Clinical Trials) Regulations 2004 (SI 2004/1031) definitions:

Adverse Event (AE)- Any untoward medical occurrence in a subject to whom a medicinal product has been administered, including occurrences which are not necessarily caused by or related to that product.

Serious Adverse Event (SAE), Serious Adverse Reaction (SAR) or Suspected Unexpected Serious Adverse Reaction (SUSAR)-Any adverse event, adverse reaction or unexpected adverse reaction, respectively, that:

- Results in death
- Is life-threatening* (subject at immediate risk of death)

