- Requires in-patient hospitalisation or prolongation of existing hospitalisation**
- Results in persistent or significant disability or incapacity, or consists of a congenital anomaly or birth defect
- Is another important medical event that may jeopardise the subject***

*'life-threatening' in the definition of 'serious' refers to an event in which the patient was at risk of death at the time of the event; it does not refer to an event which hypothetically might have caused death if it were more severe.

**Hospitalisation is defined as an inpatient admission, regardless of length of stay, even if the hospitalisation is a precautionary measure for continued observation. Hospitalisations for a pre-existing condition, including elective procedures that have not worsened, do not constitute an SAE.

***Other important medical events that may not result in death, be life-threatening, or require hospitalisation may be considered a serious adverse event/experience when, based upon appropriate medical judgement, they may jeopardise the subject and may require medical or surgical intervention to prevent one of the outcomes listed in this definition.

Adverse event inclusions and exclusions

Include:

- An increase in frequency of hypoglycaemia that is suddenly noticeable to the patient/patient's relatives
- A blood glucose reading >30 mmol/L
- Unexplained constantly raised blood glucose readings (3 consecutive readings >20mmol and over 12 hours)
- Suspicion of pump malfunction (This would be adjudicated by the educator).
- Pump site infection

Pregnancy will be recorded as an SAE so that any AEs may be identified if and when the child is born.

Do not include:

The following can occur in any patient with Type 1 diabetes and will not be classed as adverse events:

- Non-severe episodes of hypoglycaemia
- Ketonuria

Classification of severe hypoglycaemia

Defined as:

A hypoglycaemic episode leading to cognitive impairment sufficient to cause either coma or requiring the assistance of another person to recover.

Severe hypoglycaemic episodes requiring hospitalisation (as defined above) will be reported as SAEs.

Classification of diabetic ketoacidosis (DKA)

Hospitalisation and corroboration of Diabetic Ketoacidosis diagnosis will be reported as an SAE. Since all significant episodes of ketosis will need hospital admission we

can be confident of capturing all relevant episodes.

Assessment of Adverse Events

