Adverse events will be assessed for relationship to the study drug (Yes/No) and for seriousness (Yes/No). Events assessed as serious will also be reported as an SAE.

SAEs will be assessed for; seriousness, frequency, intensity, relationship to study product and relationship to pump. Expectedness of SAE's will be assessed against the reference safety information in the SmPC for the type of insulin used in the arm of the study the patient is randomised to.

The following criteria will be used when assessing SAEs: Intensity (severity):

- Mild - does not interfere with routine activities

- Moderate - interferes with routine activities

- Severe - impossible to perform routine activities

Relationship to the study product/pump:

- Unrelated - There is no evidence of any causal relationship. N.B. An alternative cause for the AE should be given.

- Unlikely - There is little evidence to suggest there is a causal relationship.

There is another reasonable explanation for the event (e.g. the participant's clinical condition, other concomitant treatment).

- Possible - There is some evidence to suggest a causal relationship. However, the influence of other factors may have contributed to the event

(e.g. the participant's clinical condition, other concomitant treatments).

- Probable - There is evidence to suggest a causal relationship and the influence of other factors is unlikely.

- Definite - There is clear evidence to suggest a causal relationship and other possible contributing factors can be ruled out.

- Not assessable - There is insufficient or contradictory information which cannot be supplemented or verified.

Reporting Procedures

All trial participants will be encouraged to contact and inform their local diabetes educator if they experience any of the medical problems outlined under SAEs or relevant AEs included (above). Any that are not picked up through general contact will be identified at follow up visits through educators enquiring about problems that the patients have had.

Relevant non serious ARs/AEs/UARs - Educators will record events on the adverse event paper CRF and database.

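### The adverse event list asks for two pump-specific events with no injection counterpart, so non-serious delivery-related harms are likely to be under-recorded in the MDI arm

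*Protocol*

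**What the plan says.** In section 8 of the protocol, *Adverse event inclusions and exclusions* gives five event types to include. Three are glycaemic and possible in either arm: a sudden rise in how often hypoglycaemia occurs, a single very high glucose value, and high values that persist without explanation. The fourth item is "Suspicion of pump malfunction (This would be adjudicated by the educator"). The fifth, which also needs a pump, is "Pump site infection".

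The exclusions that follow are non-severe hypoglycaemia and ketonuria. Injection problems appear in neither list.

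*Reporting Procedures* asks participants to contact their educator "if they experience any of the medical problems outlined under SAEs or relevant AEs included (above"). Events missed in this way are to be picked up when educators ask about problems at follow-up visits. Table 1 assigns the AE identification log to the outcome "Safety endpoints".

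The general definition of an adverse event, under *Definitions*, is wide: "Any untoward medical occurrence in a subject to whom a medicinal product has been administered", whether or not the product caused it.

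**The concern.** The trial compares two ways of delivering insulin. *Tracking and Accountability Process* says that the delivery mechanism, not the insulin, is under study. Harms that come from the delivery method are therefore part of the question and should be sought with equal effort in both arms. MDI also exposes participants to delivery-related problems: the introduction describes regimens of five or six injections a day.

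The list prompts for a device fault and a site infection only where the device is a pump. A participant with a minor pump-site infection is told to report it; one with a minor injection-site infection is not. If the adverse events are later summarised by arm as one count, part of any difference may come from what was asked for and not from what happened. An analysis plan can keep event types apart, but it cannot recover MDI events that nobody requested.

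**Working it through.** **Count of the list.** Both arms can have 3 of the 5 types (the hypoglycaemia item and the two glucose items). Pump-only: 2 of 5 (40%). Injection-only: 0 of 5. Pump-only here means by treatment received; an MDI participant who moved to a pump could have such an event and would still count in the MDI arm by randomisation.

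**Does the list govern what is recorded?** Three places bear on this.

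- *Definitions* would admit an injection-site infection.
- *Reporting Procedures* ties participants' own reports to serious events and the listed items.
- The visit enquiry is introduced as a backstop for events not already picked up. It can be read as limited to the listed items or as open.

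The amendment history records that pump site infection was added to the list on purpose, which suggests that the list was meant to do work the general definition did not. Under-recording on MDI is therefore likely, but complete non-recording is not shown.

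**Can the attribution fields repair it?** Under *Assessment of Adverse Events*, relationship to the pump is recorded for serious events. Non-serious events are assessed for relationship to the study drug and for seriousness only. Pump events can still be separated by type because they are distinct list items; unrequested injection events cannot be recovered.

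**Effect on a pooled count, if one were made.** The protocol gives no event rates, so every rate here is an assumption. Let s be the rate per participant of the three shared types, equal in both arms; m the rate of the two pump-only types on CSII; and i the rate of the equivalent injection events on MDI. Take the extreme case in which none of the injection events is recorded.

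- Recorded ratio, CSII to MDI: (s + m)/s = 1 + m/s
- Ratio with equal ascertainment: (s + m)/(s + i)
- Factor due to the asymmetry alone: (s + i)/s = 1 + i/s

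| Assumed m/s | Recorded ratio |
|---|---|
| 0.1 | 1.1 |
| 0.5 | 1.5 |
| 1 | 2.0 |

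The recorded ratio is not all artefact, because pump events are real harms. If injection counterparts are rare (i near 0), nearly all of the excess is genuine. If they are as common as the pump events (i = m), all of it is artefact.

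**Which planned results are touched?** Section 2 names the adverse event outcomes as severe hypoglycaemia, admissions for it, and DKA. The secondary endpoints list hypoglycaemia and DKA. Section 9 models HbA1c, hypoglycaemic episodes, insulin use, weight, lipids and proteinuria. All can be observed in either arm, and none uses the pooled list.

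**The case against.** The strongest reply is that nothing planned depends on this. The protocol has no pooled count, rate or test of adverse events by arm, and how adverse event tables are grouped is properly left to the analysis plan, which is not at hand. That stands, and it sets the weight of the point.

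Some stronger readings are tempting, and the document does not support them.

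- *That the trial's adverse event comparison is weighted against CSII by construction.* No such comparison is planned.
- *That pump-only events could drive early stopping.* The example in *Safety & Efficacy Parameters* is hypoglycaemia or DKA, both possible in either arm. Section 10 has the DMEC consider adverse events but does not say that it compares totals.
- *That injection-site events will certainly go unrecorded.* The wide definition and the visit enquiry may capture some, and one that needs admission is a serious event in either arm.
- *That the inflation can be put at 5/3 = 1.67.* This assumes the same rate for every listed type, from a single glucose reading to a site infection. Nothing in the protocol supports that.
- *That adjudication by an unblinded educator adds to the bias.* A suspected pump malfunction arises only in pump users, so there is no between-arm judgement to distort. If adjudication removes suspicions, it lowers the CSII count.
- *That recording pump events is itself a fault.* It is proper safety capture for this intervention. The weakness is the missing counterpart.

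What survives is the unequal prompting. It is fixed by the collection wording, so it is a matter for the protocol and not only for the tables.

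**Conclusion.** The point holds as a minor asymmetry in ascertainment. The list solicits two pump-specific events and no injection equivalent, and reporting is steered to the list, so non-serious delivery-related harms are likely to be under-recorded on MDI. Any crude adverse event total by arm would need that caveat. The primary endpoint, the named safety outcomes and the stopping example are not affected.

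The size cannot be derived from the document. The range of 1.1 to 2.0 for a pooled ratio rests on an assumed m/s of 0.1 to 1, equal shared-type rates in both arms, and no injection events recorded. It illustrates how the ratio behaves and is not an estimate of bias.

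The protocol accepts the principle elsewhere: under *Minimisation of Bias*, insulin dose is collected by recall in both arms because the pump's automatic record would make the two measurements differ. Minor severity; a cheap improvement.

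**What to change.** Reword the two items so that they apply to both arms: *suspected malfunction of the insulin delivery device (pump, infusion set or pen)* and *infection at an infusion or injection site*. Carry the same wording into the adverse event form and the participants' contact card.

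In DMEC and final tables, show delivery-specific events by type in their own rows alongside the adverse event summary. Do not remove them from it: they are real harms of the delivery method, and leaving them out would understate the harms of CSII. For events collected under the current list, separate rows make the comparison readable but do not restore MDI events that were never sought, so a footnote should say so.

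The cost is a change of form and guidance wording and a few more adverse event forms in the MDI arm. Sample size, endpoints and the primary analysis do not change.
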